4.2 EXCLUSION CRITERIA

Exclusion criteria will be assessed within 28 days of starting study treatment:

1. Participation in another clinical study with an investigational product during the last 28 days.
2. Concurrent enrollment in another clinical study, unless it is an observational (non-interventional) clinical study or during the follow-up period of an interventional study.
3. Receipt of the last dose of anticancer therapy (chemotherapy, immunotherapy, endocrine therapy, targeted therapy, biologic therapy, tumor embolization, monoclonal antibodies) ≤ 28 days prior to

the first dose of study drug. If sufficient wash-out time has not occurred due to the schedule or PK properties of an agent, a longer wash-out period will be required, as agreed by AstraZeneca, Aravive, and the investigator.

4. Any unresolved toxicity NCI CTCAE Grade ≥ 2 from previous anticancer therapy with the exception of alopecia, vitiligo, and the laboratory values defined in the inclusion criteria.
 - a. Patients with Grade ≥ 2 neuropathy will be evaluated on a case-by-case basis after consultation with the primary investigator.
 - b. Patients with irreversible toxicity not reasonably expected to be exacerbated by treatment with durvalumab may be included only after consultation with the primary investigator.
5. Any concurrent chemotherapy, IP, biologic, or hormonal therapy for cancer treatment.
6. Major surgical procedure (as defined by the Investigator) within 28 days prior to the first dose of IP. Note: Local surgery of isolated lesions for palliative intent is acceptable.
7. History of allogenic organ transplantation.
8. Active or prior documented autoimmune or inflammatory disorders (including inflammatory bowel disease [e.g., colitis or Crohn's disease], diverticulitis [with the exception of diverticulosis], systemic lupus erythematosus, Sarcoidosis syndrome, or Wegener syndrome [granulomatosis with polyangiitis, Graves' disease, rheumatoid arthritis, hypophysitis, uveitis, etc]). The following are exceptions to this criterion.
 - a. Patients with vitiligo or alopecia.
 - b. Patients with hypothyroidism (e.g., following Hashimoto syndrome) stable on hormone replacement.
 - c. Any chronic skin condition that does not require systemic therapy.
 - d. Patients without active disease in the last 5 years may be included but only after consultation with the primary investigator.
 - e. Patients with celiac disease controlled by diet alone.
9. Uncontrolled intercurrent illness, including but not limited to, ongoing or active infection, symptomatic congestive heart failure, uncontrolled hypertension, unstable angina pectoris, cardiac arrhythmia, interstitial lung disease, serious chronic gastrointestinal conditions associated with diarrhea, or psychiatric illness/social situations that would limit compliance with study requirement, substantially increase risk of incurring AEs or compromise the ability of the patient to give written informed consent.
10. Any medical, social, or psychological condition that would interfere with evaluation of study treatment or interpretation of patient safety or study results.
11. Active infection including tuberculosis (clinical evaluation that includes clinical history, physical examination and radiographic findings, and TB testing in line with local practice), hepatitis B (known positive HBV surface antigen (HBsAg) result), hepatitis C, or human immunodeficiency virus (positive HIV 1/2 antibodies). Patients with a past or resolved HBV infection (defined as the presence of hepatitis B core antibody [anti-HBc] and absence of HBsAg) are eligible. Patients positive for hepatitis C (HCV) antibody are eligible only if polymerase chain reaction is negative for HCV RNA.
12. History of another primary malignancy except for the following histories.
 - a. Malignancy treated with curative intent and with no known active disease ≥ 5 years before the first dose of IP and of low potential risk for recurrence.
 - b. Adequately treated non-melanoma skin cancer or lentigo maligna without evidence of disease.
 - c. Adequately treated carcinoma in situ without evidence of disease.
13. History of leptomeningeal carcinomatosis.

14. Brain metastases or spinal cord compression. Patients with suspected brain metastases at screening should have a MRI (preferred) or CT each preferably with intravenous (IV) contrast of the brain prior to study entry.
15. Mean QT interval corrected for heart rate using Fridericia's formula (QTcF) ≥ 470 ms.
16. Current or prior use of immunosuppressive medication within 14 days before the first dose of durvalumab or AVB-S6-500. The following are exceptions to this criterion:
 - a. Intranasal, inhaled, topical steroids, or local steroid injections (e.g., intra articular injection)
 - b. Systemic corticosteroids at physiologic doses not to exceed 10 mg/day of prednisone or its equivalent.
 - c. Steroids as premedication for hypersensitivity reactions (e.g., CT scan premedication).
17. Receipt of live attenuated vaccine within 30 days prior to the first dose of IP. Note: Patients, if enrolled, should not receive live vaccine whilst receiving IP and up to 90 days after the last dose of IP.
18. Female patients who are pregnant or breastfeeding or of reproductive potential who are not willing to employ effective birth control from screening to 180 days after the last dose of durvalumab + AVB-S6-500 combination therapy.
19. Known allergy or hypersensitivity to any of the study drugs or any of the study drug excipients.
20. Unresolved partial or complete small or large bowel obstruction
21. Judgment by the investigator that the patient is unsuitable to participate in the study and the patient is unlikely to comply with study procedures, restrictions and requirements.

4.3 WITHDRAWAL OF PATIENTS FROM STUDY TREATMENT AND/OR STUDY

4.3.1 PERMANENT DISCONTINUATION OF DURVALUMAB + AVB-S6-500

An individual subject will not receive any further investigational product if any of the following occur in the patient in question.

1. Withdrawal of consent or lost to follow-up.
2. Adverse event that, in the opinion of the investigator, contraindicates further dosing.
3. Patient is determined to have met one or more of the exclusion criteria for study participation at study entry and continuing investigational therapy might constitute a safety risk.
4. Pregnancy or intent to become pregnant.
5. Any AE that meets criteria for discontinuation as defined in **Section 6.3**.
6. Clinically significant dose-limiting toxicity (DLT) that is attributable to both drugs. Durvalumab or AVB-S6-500 may be held individually due to a DLT while dosing with the other drug continues if the DLT is attributable to only one drug (See **Section 6.2** for definition of DLT and **Section 6.3** for individual drug dose holds).
7. Grade ≥ 3 infusion reaction.
8. Patient noncompliance that, in the opinion of the investigator, warrants withdrawal; e.g., refusal to adhere to scheduled visits.
9. Initiation of alternative anticancer therapy including another investigational agent.
10. Confirmation, per irRC, of PD and investigator determination that the patient is no longer benefiting from treatment with durvalumab and AVB-S6-500. See **Section 7.2**.
11. Subjects who are discontinued from further receipt of both investigational products, regardless of the reason (withdrawal of consent, due to an AE, other), will be identified as having permanently discontinued treatment. Patients who are permanently discontinued from receiving investigational product will be followed for safety per Schedule of Assessments, including the collection of any protocol-specified blood specimens, unless consent is withdrawn, or the patient is lost to follow-

up or enrolled in another clinical study. All patients will be followed for survival. Patients who decline to return to the site for evaluations will be offered follow-up by phone every 6 months as an alternative.

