6. TREATMENT PLAN

6.1 PROCEDURES FOR RANDOMIZATION

Subjects will be recruited from the Department of Gynecologic Oncology and Reproductive Medicine at The University of Texas MD Anderson Cancer Center. Patients with platinum resistant high grade ovarian, primary peritoneal, or fallopian tube cancers will be screened by the designated research staff and/or study investigators for eligibility. Interested patients will be approached and provided information regarding the study and potential eligibility and participation. After informed consent, screening evaluation will be performed to determine eligibility. Patients may elect to leave the study at any time.

We will enroll up to 30 evaluable subjects with platinum-resistant EOC at an expected rate of 3 subjects per month. Subjects will be evaluable for the primary objective once they have completed one cycle of combination therapy at the RP2D. Up to 12 evaluable subjects will be enrolled into the dose de-escalation combination phase (Safety Lead-in) to determine the RP2D. Once the RP2D is determined, subsequent subjects will be randomized to monotherapy arms as described below. To replace patients that are registered but do not proceed to treatment (e.g. screen failures), an additional 15 patients may be

registered; however, a maximum of 30 evaluable patients will be treated as per the protocol. Subjects will be treated until disease progression or until unacceptable toxicity. We will follow all patients for at least 12 months, and we will employ safety and efficacy monitoring rules as described in **Section 9.2.1** and **Section 9.2.2**.

Following RP2D determination, we will randomly assign patients to one of two monotherapy treatment arms (durvalumab or AVB-S6-500) at a ratio of 1 (durvalumab) to 3 (AVB-S6-500). All patients, with the exception of any who meet discontinuation criteria, will then receive combination treatment regimen.

Randomization will be carried out using CORe.

Subjects who are incorrectly enrolled but have not been initiated on treatment will be withdrawn from the study. Such subjects will be replaced. Any subjects who are incorrectly enrolled and randomized and initiated on therapy will be reported to the IRB as a protocol violation. Such subjects will be evaluated on an individual basis by the PI and the decision to continue treatment or withdraw will be based on an analysis of risk/benefit for the subject.

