6.3.3 COMBINATION TREATMENT REGIMEN

In addition to the individual toxicity management guidelines for durvalumab and AVB-S6-500 described above management of any potential overlapping toxicities that may occur following treatment with this combination must be considered. For AEs that are considered at least partly due to administration of durvalumab or AVB-S6-500, treat each of the toxicities with maximum supportive care (including holding the agent suspected of causing the toxicity where required). If the symptoms promptly resolve with supportive care, consideration should be given to continuing the same dose of durvalumab or AVB-S6-500 along with appropriate continuing supportive care.

For these subjects, once the AE resolves to permit resumption of the investigational combination, if the AE recurs at a dose-limiting severity, AVB-S6-500 and durvalumab dosing should be held until the recurrence until the AE resolves to Grade 1 or baseline. The AE should resolve to Grade 1 or baseline within 21 days for the subject to be considered for continued treatment. If the AE does not resolve to Grade 1 or baseline within 21 days, the investigator should consult the MDACC IND Office to determine feasibility of continued treatment with AVB-S6-500 and durvalumab.

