11. STUDY MANAGEMENT

11.1 MONITORING OF THE STUDY

The study will be monitored by the M.D. Anderson IND office and a protocol specific monitoring plan will be followed. We will monitor unacceptable toxicity (defined as grade 3 or greater treatment-related AEs or discontinuation of the study regimen due to side effects) independently in each monotherapy treatment arm and in subsequent combination treatment, guarding against an unacceptable toxicity rate of 40% or higher (based on published studies employing combination of other Anti-PD1/PDL1 agents), using the methods of Thall et al.[64].

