			
For Grade 2:
 
Consider symptomatic treatment, including hydration, electrolyte replacement, dietary changes (e.g., American Dietetic Association colitis diet), and loperamide and/or budesonide.
 
 – Promptly start prednisone 1 to 2 mg/kg/day PO or IV equivalent. – If event is not responsive within 2 to 3 days or worsens despite prednisone at 1 to 2 mg/kg/day PO or IV equivalent, consult a GI specialist for consideration of further workup, such as imaging and/or colonoscopy, to confirm colitis and rule out perforation. – If still no improvement within 2 to 3 days despite 1 to 2 mg/kg IV methylprednisolone, promptly start immunosuppressant agents such as infliximab at 5 mg/kg IV, may be repeated at 2 and 6 weeks after initial dose at the discretion of the treating provider.. Caution: it is important to rule out bowel perforation and refer to infliximab label for general guidance before using infliximab. – Consider, as necessary, discussing with study physician if no resolution to Grade ≤ 1 in 3 to 4 days. 
For Grade 3 or 4:
 
Grade 3
 
 • For patient treated with PDL-1 inhibitors, hold study drug/study regimen until resolution to Grade ≤ 1; study drug/study regimen can be resumed after completion of steroid taper. Permanently discontinue study drug/study regimen for Grade 3 if toxicity does not improve to Grade ≤ 1 within 14 days. • Permanently discontinue study 
Promptly initiate empiric IV methylprednisolone 1 to 2 mg/kg/day or equivalent.
 
 – Monitor stool frequency and volume and maintain hydration. – Urgent GI consult and imaging and/or colonoscopy as appropriate. – If still no improvement within 2 to 3 days, promptly add further immunosuppressants (e.g., infliximab at 5 mg/kg IV, may be repeated at 2 and 6 weeks after initial dose at the discretion of the treating provider). Caution: Ensure GI consult to rule out bowel perforation and refer to infliximab label for general guidance before using infliximab. If perforation is suspected, consult a surgeon experienced in abdominal surgery immediately without any delay.

Adverse Events	Severity Grade of the Event	Dose Modifications	Toxicity Management

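### For a few overlapping toxicities the protocol both stops and allows re-dosing, with no stated precedence, so exposure and the AE-discontinuation proportion depend on the passage followed

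*Combined protocol and SAP*

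**What the plan says.** Section 4.3.1 opens its list with "An individual subject will not receive any further investigational product if any of the following occur in the patient in question". Item 6 of that list is "Clinically significant dose-limiting toxicity (DLT) that is attributable to both drugs"; it adds that one drug may be held alone if the DLT is attributable to that drug only. Item 7 is any infusion reaction of Grade 3 or higher. Item 5 refers to the discontinuation criteria of Section 6.3, which lead on to Appendix A.

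Section 6.2 counts Grade 3 diarrhea or colitis as a DLT with no condition on duration.

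For the same Grade 3 event, the colitis row of Appendix A says "For patient treated with PDL-1 inhibitors, hold study drug/study regimen until resolution to Grade" 1 or lower. It allows resumption after the steroid taper and requires a permanent stop only if there is no such improvement within 14 days (or in other circumstances, such as intestinal perforation).

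On recurrence, Section 6.3.3 says "if the AE recurs at a dose-limiting severity, AVB-S6-500 and durvalumab dosing should be held until" resolution, and then "The AE should resolve to Grade 1 or baseline within 21 days for the subject to be considered for continued treatment". Beyond 21 days the IND Office is consulted on whether continuing is feasible. The general considerations of Appendix A instead call for permanent discontinuation of recurrent Grade 3 immune-mediated events that need systemic immunosuppression.

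On infusion reactions, Section 5.1.3 stops for Grade 3 or higher but tolerates one Grade 3 reaction that resolves within 6 hours without prophylaxis. Appendix A stops for any Grade 3 or 4 reaction.

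Sections 9.2 and 9.2.1 plan an estimate, with a 90% confidence interval, of the proportion discontinuing for adverse events (treatment-related ones in 9.2.1).

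**The concern.** Two patients with the same event and the same course can be handled in opposite ways, each in full compliance with the protocol. One is recorded as a discontinuation for an adverse event and receives no more drug; the other is recorded as a hold and goes on. That is first a patient-safety matter, because the investigator has no way to tell which instruction binds.

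It is also a statistical matter. The toxicity profile is the primary objective, and the discontinuation proportion is one of its planned summaries. If the count depends on which section was consulted, it no longer describes the regimen alone. Exposure after the event differs too. Any effect on response or irPFS would come through exposure, and the documents give nothing from which to size it.

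**Working it through.** The plan states no figure that depends on this point, so there is none to reproduce. The check is a side-by-side reading, followed by a small calculation for scale.

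**Step 1. Same event, different instructions.**

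| Event | Passage that ends treatment | Passage that allows more treatment |
|---|---|---|
| Grade 3 diarrhea/colitis, clinically significant, attributed to both drugs, at Grade 1 by day 10 | 4.3.1 item 6 (a DLT under 6.2; no resolution window) | Appendix A colitis row: resume after steroid taper, since day 10 is within 14 days |
| Recurrent Grade 3 immune-mediated event of dose-limiting severity needing systemic immunosuppression, at Grade 1 by day 18 | Appendix A general considerations: permanent discontinuation | 6.3.3: hold, then consider continuing, since day 18 is within 21 days |
| One Grade 3 infusion reaction, no prophylaxis, resolved within 6 hours | 4.3.1 item 7; Appendix A infusion-reaction table | 5.1.3 |

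The days of resolution are chosen for illustration. Each row satisfies the conditions of both passages, so these are true overlaps.

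**Step 2. Is there a precedence rule?** None is stated. Section 4.3.1 does not settle it by itself: item 5 leads through Section 6.3 to Appendix A, where the first patient above does not meet the criterion for stopping, while item 6 of the same list stops her. Section 6.3.1 describes the guidelines as help for clinical judgment and does not rank them against 4.3.1 or 6.3.3.

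**Step 3. How far does the overlap reach?** Item 6 needs three things together: a DLT, clinical significance (not defined for this purpose), and attribution to both drugs. Section 6.2 evaluates DLTs in the safety lead-in over the first 6 weeks. Many Grade 3 related events are not DLTs, for example a Grade 3 non-immune event that resolves to Grade 1 or baseline within 30 days. For several others, including Grade 3 pneumonitis, nephritis, pancreatitis, neurotoxicity and myocarditis, Appendix A itself stops treatment, so it offers no route to resumption.

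**Step 4. Scale for the discontinuation proportion.** Inputs: n = 5, because Section 3.1 says enrollment ended after the 5th evaluable subject completed lead-in treatment; n = 27 is the original evaluable target in Section 9. The interval method is not named, so I assume the exact (Clopper-Pearson) 90% interval:

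- lower limit = 5th percentile of Beta(x, n − x + 1), or 0 if x = 0
- upper limit = 95th percentile of Beta(x + 1, n − x)

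For x = 0 the upper limit is 1 − 0.05^(1/n). At n = 5 this is 1 − 0.05^0.2 = 0.451. For x = 1 the lower limit is 1 − 0.95^(1/n). At n = 5 this is 1 − 0.95^0.2 = 0.010.

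| n | No patient counted as discontinued | One patient counted as discontinued |
|---|---|---|
| 5 | 0/5 = 0% (0 to 45.1%) | 1/5 = 20% (1.0 to 65.7%) |
| 27 | 0/27 = 0% (0 to 10.5%) | 1/27 = 3.7% (0.2 to 16.4%) |

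**Step 5. What does not move.** A DLT is counted when it meets Section 6.2, whether or not the patient is later re-dosed, so the dose-finding counts are not directly changed. The Section 11.1 toxicity rate hardly moves for Grade 3 related events, because they count there whether or not treatment stops.

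**The case against.** The best defence is that the passages can be ranked. Section 4.3.1 is mandatory in tone, whereas Appendix A offers recommendations and says only that drug can be resumed after Grade 3 colitis. An investigator could apply the strictest applicable rule and never breach the protocol. This is a workable reading, but it is the reader's own: no precedence is written down, and it would leave the resumption provisions without effect for the overlapping events. It narrows the problem without removing it.

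It is also fair that enrollment ended after five evaluable subjects, so an amendment cannot change exposure already given. That shapes the remedy; it does not make the passages agree.

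Three stronger inferences are tempting, and the documents do not support them.

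- **A further stopping rule from Sections 6.1 and 11.1.** Section 6.1 says "Subjects will be treated until disease progression or until unacceptable toxicity", and Section 11.1 is the only place that defines that last term: "We will monitor unacceptable toxicity (defined as grade 3 or greater treatment-related AEs or discontinuation of the study regimen due to side effects". A reader might conclude that every Grade 3 related event ends treatment. But 11.1 defines an endpoint for monitoring a rate against 40%, and it includes discontinuation for side effects. Carried into 6.1, it would make 6.1 circular. The shared term is a minor wording point.
- **Section 6.3.3 as permission to resume after a first dose-limiting event.** Its text is "once the AE resolves to permit resumption of the investigational combination, if the AE recurs at a dose-limiting severity". The dose-limiting severity belongs to the recurrence; the first occurrence may have been milder or due to one drug. The conflict there concerns recurrence only.
- **A conflict for all Grade 3 related events.** A reader might suppose that three resolving Grade 3 related events in 15 patients would give 3/15 (20%) under one passage and 0/15 under another. The first figure needs all three to be clinically significant DLTs attributed to both drugs. The second fails for the event types in Step 3 and for Grade 3 infusion reactions, for which Appendix A stops treatment even if they resolve.

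**Conclusion.** The re-dosing rules contradict each other for three defined overlaps: a clinically significant Grade 3 diarrhea or colitis that is a DLT attributed to both drugs; certain recurrent Grade 3 immune-mediated events; and a single, quickly resolving Grade 3 infusion reaction. Nothing in the documents says which passage prevails.

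The consequence falls on exposure and on the proportion discontinuing for adverse events. At five patients, one patient classified differently shifts the estimate by 20 percentage points; at the original 27 it would be 3.7 points. Both figures assume exactly one affected patient and an exact interval. The documents do not show that any such patient occurred, so they indicate sensitivity, not an estimated bias. I take no view on which clinical rule is right.

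**What to change.** Reconcile Section 4.3.1 items 6 and 7, Section 5.1.3, Section 6.3.3 and Appendix A, so that one passage governs re-dosing for these events and the others refer to it. Which rule that passage contains is for the clinical team.

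For patients already treated, record which passage governed each hold or discontinuation, and report this next to the discontinuation proportion. This is the useful part if no one remains on treatment.

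Optionally, give the Section 11.1 monitoring endpoint a different name from the treatment-ending term in Section 6.1.

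The cost is amendment wording plus a short look-back at recorded holds and stops. No new patients or assessments are needed.
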